8.3. Determination of Clinical Response

Among patients with measurable/evaluable disease, response determination will be made according to the RECIST criteria:

Complete Response (CR):	Disappearance of target lesion, confirmed at 4 weeks
Partial Response (PR):	30% decrease in longest dimension of target lesion, confirmed at 4 weeks
Stable Disease (SD):	Neither PR nor PD
Progressive Disease (PD):	20% increase in longest dimension of target lesion; no CR, PR, or SD documented before increased disease.

The exact binomial confidence interval for the proportion of subjects with a clinical response of CR or PR will be calculated.

9. PATIENT WITHDRAWAL

Patients may be removed from the study for the following reasons:

- DLT as defined in Protocol Section 6.
- Patient voluntarily decides to withdraw.
- Patient non-compliance with the study protocol.
- Intercurrent disease which in the opinion of the patient's treating physician would affect the ability of the patient to continue on the clinical study.

In the event of withdrawal due to toxicity, a patient will be requested to have safety evaluations performed as per the protocol for a one year duration post treatment. This may include having up to 90 mL of blood drawn for immunologic testing.

10. STUDY CONDUCT AND ETHICAL AND REGULATORY CONSIDERATIONS

10.1. Departure from the Protocol

There should be no departure from the protocol if at all possible. If an emergency occurs that requires departure from this protocol, the investigator or other physician in attendance in such an emergency will, if circumstances and time permit, contact the principal investigator, or in his absence, [name], Medical Director, immediately by [contact] (cell phone). Such contacts with the principal investigator will be made to permit a decision as to whether or not the patient will be continued on the study. Such departures need to be clearly documented and reported to the Institutional Review Board (IRB) and the Etubics Corporation by the principal investigator.

10.2. Informed Consent

In accordance with guidelines in the Federal Register, Vol. 48, No. 17, 1982, pp. 8951-2, all patients are required to sign a statement of informed consent. This phase I/II study involves research that presents risk, but holds the prospect of direct benefit to the individual patient (46.405-45 Code of the Federal Regulations part 46). The investigator will report to the IRB and Etubics Corporation will report to FDA changes in the research protocol and all unanticipated problems involving risks to human patients and others, and no changes will be made in the research activity without IRB approval.

10.3. Institutional Review

This study must be approved by the site's IRB. IRB approval of the protocol and the informed consent form for this study must be given in writing. The IRB must also approve any significant changes to the protocol as well as a change of principal investigator. Records of all study review and approval documents must be kept on file by the investigator and are subject to FDA inspection during or after completion of the study. Adverse events must be reported to the IRB. The IRB will receive notification of the completion of the study and final report within three months of study completion or termination. The investigator must maintain an accurate and complete record of all submissions made to the IRB, including a list of all reports and documents submitted.

10.4. Documentation and Monitoring

Data will be collected for all patients signing consent. Accurate completion of the computer data forms for all patients is the responsibility of the investigator.

10.4.1 Case Report Forms

Case Report Forms (CRFs) are used to record study data and are an integral part of the study and subsequent reports. Therefore, all reports must be legible and complete. All forms should be filled out using a black ballpoint pen. Errors should be lined out but not obliterated and the correction inserted, initialed, and dated by the principal investigator, co-investigators, study coordinator, or data manager. A CRF must be completed and signed by the principal investigator for each patient enrolled, including those removed from the study for any reason. The reason for removal must be noted on the Final Report Form by the investigator for each patient. CRFs must be kept current to reflect patient status at each phase during the course of the study. Patients are not to be identified on CRFs by name; appropriate coded identification and patient initials must be used. The investigator must keep a separate log of patient names and addresses. This log is subject to FDA inspection. Because of the potential for errors, inaccuracies, and illegibility in transcribing data onto CRFs, originals of laboratory and other test results must be kept on file with patient's CRFs or clinical chart. CRFs and copies of test results must be available at all times for inspection by the FDA.

10.4.2 Maintenance of Study Documentation

The following will be maintained:

- a. Case Report Forms - which must be kept legible, accurate, and up-to-date.
- b. Patient Files/Signed Informed Consent - which substantiates the data entered on the case report forms for all required test and evaluation procedures and verifies that the patient has signed an informed consent to enter the study.
- c. Patient Exclusion Record - which should reflect the reason any patient was screened and found ineligible for the study.
- d. Monitoring Log - listing dates of monitor visits.
- e. Regulatory Documents - including protocol, investigator brochure, FDA Form 1572, CVs, IRB correspondence, IRB approval/renewals and IRB approved consent form.
- f. Adverse Event Report Form - which should explain any serious or unexpected adverse experiences.

All study documentation pertaining to the conduct of the study must be kept on file by the investigator for a period of 2 years following the date a marketing application is approved for the drug for the indication for which it is being investigated; or, if no application is to be filed or if the application is not approved for such indication, until 2 years after the investigation is discontinued and FDA is notified. The sponsor will notify the investigator if a marketing application is approved or if the investigation is discontinued and the FDA notified.

10.5. Monitoring of the Protocol

An Etubics Corporation representative will conduct a site initiation visit and will review protocol documents with the investigators and their staff. During the study, the Etubics monitor will visit the site regularly to check the completeness of study files, the accuracy of data entries on the CRFs, and adherence to the protocol and to Good Clinical Practice (GCP). Key study personnel must be available to assist the monitor during these visits. The investigator must maintain source documents for each subject in the study. The investigator must also keep the original informed consent form signed by every patient. The investigator must give the monitor access to all relevant

source documents to verify data entries on CRFs. No information in source documents about the identity of subjects will be disclosed.

This is a phase I/II clinical study with more than minimal risk and as such will be monitored for the occurrence of a greater frequency of adverse events (AEs). The principal investigator will continuously monitor the data and safety of all subjects enrolled. All grades of toxicities will be recorded.

Safety assessments will consist of monitoring all AEs including serious adverse events (SAEs), the regular monitoring of hematology, serum chemistry, and routine monitoring of vital signs and physical condition. AE monitoring should occur from the time of informed consent to 30 days after the last dose of study drug. For those subjects who discontinue study participation prior to receiving study drug, AE and SAEs will be collected through the time of discontinuation.

Toxicity will be assessed using the NCI CTCAE version 4.0. Refer to Protocol Section 7.3.2.

An AE is any adverse change from the study patient's baseline (pretreatment) condition, including any clinical or laboratory test abnormality that occurs during the course of the proposed clinical study after treatment has started.

Events are classified as SERIOUS if they meet any of the following criteria [per the US Code of Federal Regulations (CFR) 21 CFR 312.32 and the recommendations of the International Conference on Harmonization (ICH)]:

An SAE is any sign, symptom or medical condition that emerges during the study or during a post-study follow-up period that 1) was not present at the start of the study and is not a chronic condition that is part of the patient's medical history, OR 2) was present at the start of the study or as part of the patient's medical history but worsened in severity and/or frequency during study participation, AND that meets any of the following regulatory serious criteria:

- any death
- any life-threatening event, i.e., an event that places the patient, in the view of the investigator, at immediate risk of death from the event as it occurred (does not include an event that, had it occurred in a more severe form, might have caused death)
- any event that requires or prolongs in-patient hospitalization
- any event that results in persistent or significant disability/incapacity
- any congenital anomaly/birth defect diagnosed in a child of a patient who participated in this study and received investigational drug
- other medically important events that in the opinion of the investigator may jeopardize the patient or may require intervention to prevent one of the other outcomes listed in the definition above (e.g. allergic bronchospasm requiring intensive treatment in an emergency room, convulsions occurring at home that do not require in-patient hospitalization, any blood dyscrasias, or the development of drug dependency or drug abuse).

10.6. CTCAE Term (AE description) and Grade

The descriptions and grading scales found in the revised NCI CTCAE version 4.0 will be utilized for AE reporting. A copy can be downloaded from the CTEP web site (<http://ctep.cancer.gov>).

The CTCAE displays Grades 1 through 5 with unique clinical descriptions of severity for each AE based on the following guideline:

Grade 1	Mild AE
Grade 2	Moderate AE
Grade 3	Severe AE
Grade 4	Life-threatening or disabling AE
Grade 5	Death related to AE

10.7. Assessing Causality

Investigators are required to assess whether there is a reasonable possibility that study medications caused or contributed to an adverse event. The following general guidance may be used.

- Yes:** if the temporal relationship of the clinical event to study drug administration makes a causal relationship possible, and other drugs, therapeutic interventions or underlying conditions do not provide a sufficient explanation for the observed event.
- No:** if the temporal relationship of the clinical event to study drug administration makes a causal relationship unlikely, or other drugs, therapeutic interventions or underlying conditions provide a sufficient explanation for the observed event.

10.8. Serious Adverse Event Reporting

All AEs that are classified as serious, unexpected and related or possibly related, will be recorded on the MedWatch 3500A form and reported within 24 hours of learning of the event to Etubics Corporation. The form should be completed as much as possible but should not be held until all information is available. Additional information and/or corrections may be submitted as they are obtained. The investigator will follow SAEs until resolution, a return to baseline condition or stabilization or 30 days after the last subject is enrolled whichever occurs first. SAEs that are ongoing at the time of clinical database closure will be recorded as unresolved.

All study-related deaths should be reported to the IRB within 24 hours; all other serious adverse experiences should be reported to the IRB within 5 business days. All deaths, whether considered study-related or not, must also be reported immediately to Etubics Corporation, additional information may be requested from the treating institution. Deaths believed to be related to disease progression will not be reported to the FDA as SAEs, as these deaths are an anticipated outcome of the disease; however, all deaths will be reported to the FDA in the annual reports.

MedWatch 3500A Reporting Guidelines:

In addition to completing appropriate patient demographic and suspect medication information, the report should include the following information within the Event Description (section 5) of the MedWatch 3500A form:

- Treatment regimen (dosing frequency, combination therapy)
- Protocol description (and number, if assigned)
- Description of event, severity, treatment, and outcome, if known
- Supportive laboratory results and diagnostics
- Investigator's assessment of the relationship of the adverse event to each investigational product and suspect medication

Follow-up information:

Additional information may be added to a previously submitted report by any of the following methods:

- Adding to the original MedWatch 3500A report and submitting it as follow-up
- Adding supplemental summary information and submitting it as follow-up with the original MedWatch 3500A form

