- 3) Cohort 3: Six patients will receive Ad5 [E1-, E2b-]-CEA(6D) at a dose of 1×10^{11} particles in 0.5 mL SQ in the same thigh every 3 weeks for 3 immunizations. Immunizations site should be separated by 5 cm. A diary card will be given to each subject at the first treatment along with a ruler to record any adverse reactions for 2 days after treatment (24 hours and 48 hours post injection). The diary card will be placed in the study file. Assessment of DLT for proceeding to phase II enrollment (Cohort 4) will be made after all patients in this cohort have had a study visit at least 3 weeks after receiving their first dose of vaccine. If there is 0 or 1 DLT, then subjects may enroll in Cohort 4. If 2 patients have DLT at this dosage level, the dosage level in cohort 2 will be considered the MTD. If only 3 patients were enrolled in cohort 2, an additional 3 patients will be enrolled at that dosage before proceeding to the next level.
- 4) Phase II cohort (Cohort 4): After the MTD is established, an additional 12 patients will receive Ad5 [E1-, E2b-]-CEA(6D) at the MTD every 3 weeks for 3 immunizations.

Note: if during accrual of patients in the phase II cohort, DLT occurs at a sufficient rate such that the rate of DLT amongst the total number of patients (those treated at MTD in phase I and those in phase II) is $\geq 33\%$, then phase II will be restarted at the dosage level which is one level below the prior MTD.

- 5) Cohort 5: Six patients will receive Ad5 [E1-, E2b-]-CEA(6D) at a dose of 5×10^{11} particles SQ in 2.5 mL every 3 weeks for 3 immunizations. Assessment of DLT will be made after all patients in this cohort have had all 3 injections and been observed for at least 30 days after the last injection. If there are 0-1 DLT, then this will be declared the maximum feasible dose. If there are 2 or more DLT, then 1×10^{11} particles will be declared the MTD.

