7.1.1 General Evaluations

Weeks 0, 3, 6 (Immunization Visits):

General evaluations include medical history, Karnofsky performance status, and complete physical examination with weight by the attending physician. Any other treatments, medications, biologics, or blood products that the patient is receiving or has received since the last visit will be recorded. Patients will remain in the clinic for approximately 30 minutes following receipt of vaccine to monitor for any adverse reactions. Local and systemic reactogenicity after each dose of vaccine will be assessed daily for 3 days (on the day of immunization and 2 days thereafter) using diary cards to report symptoms and a ruler to measure local reactogenicity.

Week 9:

General evaluations include medical history, Karnofsky performance status, and complete physical examination with weight by attending physician. Any other treatments, medications, biologics, or blood products that the patient is receiving or has received since the last visit will be recorded. Immunization injection sites will be assessed.

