8. STATISTICAL CONSIDERATIONS

8.1. Safety

We will evaluate safety continuously in a cohort. We will make our overall assessment of whether to escalate to the next dose level at least 3 weeks after the last patient in the previous cohort has received their first injection. This decision will be made by the medical monitor and the Principal Investigator. A note will be generated following the assessment decision and filed in study binder. A dosage level will be considered safe if <33% patients treated at a dose level experience DLT (i.e., 0 of 3, ≤ 1 of 6, ≤ 3 of 12, or ≤ 5 of 18 patients). DLT is defined in Protocol Section 6. Safety will be evaluated in 3 or 6 patients at each dosage level in phase I. Safety will continue to be monitored among additional patients treated at the MTD in phase II. A patient will be considered evaluable for safety if treated with at least one immunization. DLTs will be observed through 9 weeks to accommodate safety evaluation of all 3 product doses.

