12. APPENDIX 1 – SCHEMA

Procedure / Test	Pre-treatment	Week 0	Week 3	Week 6	Week 9	Months 6, 9, etc. ⁱ	Off Treatment
H & P	X	X	X	X	X	X	X
Karnofsky Status	X	X	X	X	X	X	X
β-HCG ^a	X						
CBC with diff	X	X	X	X	X	X	X
PT-INR, PTT	X						
Chemistries	X	X	X	X	X	X	X
Urinalysis	X						
ANA	X				X		X
HIV	X						
Immune Monitoring ^b	X ^b	X	X	X	X	X ^b	X ^b
Antibodies to CEA/Ad5 Vector ^c		X			X		
Biological Markers ^d (i.e. CEA, CA15-3)	X ^d				X ^d	X ^d	X ^d
Brain MRI/CT Scan ^e	X						
MRI/CT Scan ^f	X ^f				X ^f	X ^f	X ^f
Immunization ^g		X	X	X			
AE Assessment ^h	X	X	X	X	X		

Key: H & P = history & physical examination, KPS = Karnofsky Performance Score, β-HCG = human chorionic gonadotrophin pregnancy test; CBC & diff = complete blood count and white blood cell differential, Chemistries = Na, K, Cl, CO₂, BUN, creatinine, Ca, total protein, albumin, total bilirubin, alkaline phosphatase, AST, ALT and glucose; ANA = antinuclear antibody, HIV = human immunodeficiency virus antibody, MRI/CT = magnetic resonance imaging/computed tomography; AE = Adverse Event

Notes:

- ^a β-HCG performed on women of childbearing potential
- ^b Immune monitoring drawn during the first clinic visit at the discretion of the investigator/immune monitoring laboratory, prior to each immunization and approximately 3 weeks after the last immunization, and will be repeated at the discretion of the investigator/immune monitoring laboratory.
- ^c Serum obtained for antibodies to CEA and Ad5 vector weeks 0 and 9.
- ^d Available serum markers (e.g., CEA or CA15-3) reviewed as available.
- ^e Brain CT scan or MRI required within 6 weeks of starting study treatment.
- ^f Available CT scans or MRI of the chest, abdomen, and/or pelvis reviewed. Imaging studies within 6 weeks of starting study treatment is preferred, however is not required. Repeat imaging conducted according to standard of care.
- ^g Immunizations may be modified so that the interval is between 20 and 28 days (3 weeks -1 day to 3 weeks +7 days). If the second and/or third immunization is delayed, the subsequent immunizations should occur no earlier than 20 days after the previous immunization.
- ^h AE monitoring from the time of informed consent to 30 days after the last dose of study drug.
- ⁱ Follow-up evaluations requested every 3 months for 1 year, while on the study.

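### Section 10.8 ends the duty to follow SAEs to outcome 30 days after the last enrolment, before that subject's planned third dose and before the AE window for a three-dose course closes

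*Combined protocol and SAP*

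**What the plan says.** All references are to the latest protocol version in the file. The same sentence on SAE follow-up also stands in the three versions before it.

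- Section 10.8 sets the end of SAE follow-up: resolution or a return to baseline, "or stabilization or 30 days after the last subject is enrolled whichever occurs first". The next sentence uses a different end point: "SAEs that are ongoing at the time of clinical database closure will be recorded as unresolved".
- Section 10.5 anchors AE collection to dosing: "AE monitoring should occur from the time of informed consent to 30 days after the last dose of study drug". Appendix 1, note h, repeats this.
- Section 8.1 sets the DLT period: "DLTs will be observed through 9 weeks to accommodate safety evaluation of all 3 product doses".
- The SAE definition in section 10.5 includes events that emerge in a post-study follow-up period.
- Section 6, item 6 allows cohort 6 (up to 10 patients) three-monthly boosters after the three initial doses.

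**The concern.** The calendar limit applies if it comes before the SAE's outcome, so it is a hard stop. It falls on the same date for every subject and takes no account of when anyone was last dosed. The protocol's other safety windows run from dosing or cover all three doses. Read literally, an SAE open on the limit date need not be followed further, whoever the subject is. An SAE that begins later, for example after a late-enrolled subject's third dose or after a booster, never carries a duty of follow-up to outcome.

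Safety is the primary objective (section 2). At stake is the completeness of the SAE record: an event may be listed without its recovery or resolution. The clause predates cohort 6 and was not adjusted when boosters were added.

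**Working it through.** **Inputs**

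- Limit: last enrolment + 30 days (section 10.8).
- Day 0 is the first immunization and day 21 the second (section 4.4). There are three doses at 3-week intervals (section 6).
- Permitted interval between doses: 20 to 28 days (section 6, item 9).
- AE window: to 30 days after the last dose (section 10.5; Appendix 1, note h).
- DLT observation: 9 weeks (section 8.1).
- Pre-treatment evaluation: within 1 month, plus or minus 2 weeks, before treatment (section 5). The available text does not define the enrolment date.
- Assumptions: enrolment on day 0 unless a lag is shown; 3 months = 91 days.

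**Check against the plan's own figure.** Dose 3 is at 2 × 21 = day 42, or week 6. Three weeks later is 42 + 21 = day 63, or week 9, which matches section 6, item 7.

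**Last subject, three doses, enrolled on day 0.** The limit is day 30.

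| Milestone | Day | Days after the limit |
|---|---|---|
| Dose 3 | 2 × 21 = 42 (2 × 20 = 40 to 2 × 28 = 56) | 12 (10 to 26) |
| End of DLT observation | 9 × 7 = 63 | 33 |
| AE window closes | 42 + 30 = 72 (70 to 86) | 42 (40 to 56) |

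**General form.** If enrolment precedes dose 1 by L days, the limit falls on day 30 − L. The gap to AE-window closure is then (day of last dose + 30) − (30 − L) = day of last dose + L.

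- One dose only, L = 0: 0 days.
- Two doses, L = 0: 21 days.
- Three doses, L = 14: 42 + 14 = 56 days.
- Three doses, L = 30: 42 + 30 = 72 days.
- Three doses, L = 44 (30 + 14): 42 + 44 = 86 days. The limit then falls on day −14, before dose 1.
- One cohort 6 booster, L = 0: the booster is at about 42 + 91 = day 133, which is 103 days after the limit. The gap to AE-window closure is 133 days.

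**Other subjects.** A subject enrolled x days before the last one, with the same lag to dose 1, has an AE window running past the limit only if x is smaller than the day of that subject's last dose. For three doses without boosters this means enrolment within 42 days (40 to 56) of the last enrolment; with one booster, within about 133 days. The accrual rate is not given, so no patient count can be derived.

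**The case against.** The strongest case on the other side is that little safety information is lost.

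- AE collection still runs to 30 days after the last dose, SAE reporting is unchanged, and "The principal investigator will continuously monitor the data and safety of all subjects enrolled".
- At week 9, "General evaluations include medical history, Karnofsky performance status, and complete physical examination with weight by attending physician", and laboratory tests are drawn. Cohort 5 must have "been observed for at least 30 days after the last injection" before its DLT assessment.
- Cohort 6 patients must have scans about every 3 months for 12 months, are followed for survival for 24 months, and have blood drawn before each immunization (section 6, items 6 and 7). These contacts would often show how an earlier SAE ended.
- DLTs are defined by event type and grade (section 6) and counted against 33% (section 8.1). Whether an SAE later resolves does not enter that count.
- The clause may be a drafting slip.

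All of this stands, and it rules out several stronger readings that a reader might infer. The documents do not support a claim that SAEs after day 30 go undetected or unreported, or that a dose decision would change. Nor is all contact after week 9 optional: the three-monthly visits in section 7.2 and the one-year evaluations after withdrawal for toxicity in section 9 are only requested, but the cohort 6 scans are required. The 12 and 42 days are distances between dates in the text. They are not periods without safety observation.

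The objection does not supply the missing duty. None of these contacts obliges the investigator to pursue an open SAE to its outcome. The database-closure sentence says how an ongoing SAE is recorded and does not extend follow-up to closure. If the clause is a slip, that is a reason to correct it, because sites work from the written text.

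**Conclusion.** The end date for SAE follow-up in section 10.8 is wrong as written and inconsistent with sections 10.5 and 8.1, Appendix 1 note h, and the sentence that follows it. For a last subject enrolled on day 0 who completes three doses, it falls 12 days before dose 3 (10 to 26) and 42 days before the AE window closes (40 to 56). These figures depend on the three-dose course: a last subject who stops after one or two doses has a gap to AE-window closure of 0 or 21 days. Any lag from enrolment to dose 1, and any booster, lengthens it.

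The consequence is limited to the lost duty to obtain the outcome of SAEs open at, or starting after, the limit date. The point ranks between minor and should-fix. No available passage cancels the clause. Part of section 10.8, after the MedWatch guidance, is missing from the public text, and the conclusion does not rely on it.

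**What to change.** Delete the 30-day calendar limit from section 10.8 and restate the duty along these lines:

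> The investigator will follow every SAE, whenever it starts during the study or its follow-up period, until it has resolved, returned to baseline or stabilized, or until the clinical database closes, if that is sooner.

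Add that the database will close no earlier than the end of the last subject's planned follow-up, and no earlier than a stated interval (for example 30 days) after the last subject's AE window closes, booster doses included. Keep the existing sentence on SAEs ongoing at closure.

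Two features matter. The wording has no limit on onset date, because the protocol's SAE definition reaches into post-study follow-up. The interval before closure prevents the database from closing on the day the AE window ends, which would leave a late SAE without follow-up again.

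The cost is one replaced clause, one added sentence and a small amount of extra SAE follow-up. The study duration in the Protocol Summary, the one-year and two-year booster texts (Protocol Summary and section 6, item 6), and the immunization and AE rows of Appendix 1 are separate passages to be reconciled. They are not part of this point, and no booster period is proposed here.
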